9.3.1 PREGNANCY FOLLOW-UP

Every female participant will take a pregnancy test on Day 1 of Stimulation. If, after testing negative at Day 1 of Stimulation (meeting inclusion criteria), a participant reports becoming pregnant during the course of the study, she will be withdrawn from further participation. There are no plans to follow participants who become pregnant while enrolled in the study.

10 DATA AND SAFETY MONITORING

10.1 [name] LAB MONITORING PLAN

The purpose of this monitoring plan is to present the [name] Lab's approach to monitoring clinical trials. The plan facilitates compliance with good clinical practice (GCP):

- a. The rights and well-being of human subjects are protected.
- b. The reported trial data are accurate, complete, and verifiable from source documents
- c. The conduct of the trial is in compliance with the currently approved protocol/amendment(s) with GCP, and with applicable regulatory requirement(s)

This section identifies key monitoring activities and specifies the data to be reviewed over the course of a clinical trial. This is a single site, investigator-initiated, clinical trial, so there will be no site monitoring plan in place.

The latest version of the approved IRB application for this clinical trial will be followed at all times. This responsibility falls into the hands of the study coordinator and research assistants. If at any time there is a deviation from protocol, the deviation from protocol log will be filled out. All team members will be trained on how and when to use this log. The most up-to-date IRB application will be on file in the Clinical Trials office in [name]. Deviations will be sent to the IRB every 4-6 weeks (if necessary).

Periodically, study staff should review 3 randomly selected informed consent forms to ensure that (1) these forms have been filled out appropriately, and (2) the consent form process was followed and properly documented. Should any consent form be in violation, the research team will perform and document a complete review of all consent forms.

Given that we are not sampling within a clinical population we do not expect suicidal ideation to be a concern. However, we will review the Beck's inventory within 24 hours and if there is any indication that a person is a danger to themselves we will notify the medical director of the Carolina Center for Neurostimulation, [name], who will respond appropriately.

AE and SAE are clearly defined in this document. Documents of AE and SAE can be found in the study binder on file in the Clinical Trials office in [name]. It is the responsibility of the study coordinator to report all events to the PI in a timely manner (see *9.3 Reporting Procedures*). All AEs and SAEs will be discussed with the PI. For our practices, we have adapted the decision tree provided by the UNC-CH IRB to assist with reporting of such events.

10.2 SAFETY OVERSIGHT

Safety oversight will be under the direction of the PI, who will review AEs in real time and make decisions regarding a participant's continuation of the clinical trial.

10.3 EARLY WITHDRAWAL OF PARTICIPANTS

10.3.1 REASONS FOR WITHDRAWAL

A study participant will be discontinued from further participation if:

- The participant fails to adhere to rules, including stress, exercise, and sleep restrictions

- The participant meets any exclusion criteria (either newly developed or not previously recognized).
- Anything that, in the opinion of the investigator, would place the participant at increased risk or preclude the participant's full compliance with or completion of the study.
- Participants experience severe discomfort during stimulation

Participants are free to withdraw from participation in the study at any time upon request.

10.3.2 DATA COLLECTION AND FOLLOW-UP FOR WITHDRAWN PARTICIPANTS

We will collect safety data on any participant discontinued because of an AE or SAE. In any case, every effort will be made to undertake protocol-specific follow-up procedures. If an AE has been reported, researchers will help the participant seek the medical care they need and a follow-up will be performed by the PI. In the case of an early withdrawal, the researcher will make a note to file indicating this.

10.4 TERMINATION OF STUDY

If a seizure occurs at the time of a study visit, a temporary hold will be placed over the study and further investigation will ensue. This could lead to stopping the study prematurely or continuing on with further safety measures in place. If two seizures are witnessed during the study visits, the entire study will be stopped prematurely. These individuals would be referred for further medical attention. It is very unlikely that a seizure will occur, given that previous studies using tDCS in patients with depression and schizophrenia have had no seizures occur (Berlim et al., 2013, Brunelin et al., 2012).

The study will also be stopped (at least temporarily) if studies provide evidence that transcranial current stimulation caused brain damage or other harmful effects on subjects, either short-term or long-term. Examples of findings that might trigger a safety review are the number of SAEs overall, the number of occurrences of a particular type of SAE, severe AEs/reactions, or increased frequency of events.

The reasons for stopping the study and asking for further investigation include:

- If a seizure occurs during a study visit, a temporary hold will be placed on the clinical trial

The IRB will also be informed promptly and provided the reason(s) for the termination of suspension of by the investigator, as specified by the applicable regulatory requirement(s).

Berlim, M. T., Van den Eynde, F., & Daskalakis, Z. J. (2013). Clinical utility of transcranial direct current stimulation (tDCS) for treating major depression: a systematic review and meta-analysis of randomized, double-blind and sham-controlled trials. *Journal of psychiatric research*, 47(1), 1-7.

11 SAFETY & REPORTING

It is important to assess safety over the course of this study. This section describes in detail how safety is assessed, reporting of Adverse Events, Serious Adverse Events, and Unanticipated Problems. This section is a reference for internal use.

11.1 SAFETY PARAMETERS

STIMULATION SIDE EFFECTS. A stimulation adverse effects questionnaire used in previous studies will be administered at the end of each stimulation session. This questionnaire will be used as a safety measure and to collect data on participant experience. The adverse effects questionnaire asks participants to respond on a 4-point Likert scale on the severity of symptoms experienced during the stimulation session (1 = absent, 2 = mild, 3 = moderate, 4 = severe). The side effects listed are headache, neck pain, scalp pain, tingling, itching, ringing/buzzing noise, burning sensation, local redness, sleepiness, trouble concentrating, improved mood, worsening of mood, dizziness, flickering lights, and other (specify). Participants are also asked to rate on a 5-point Likert scale how related they believe the side effects to be to stimulation (1 = no relation, 2 = remote, 3 = possible, 4 = probable, 5 = definite).

In addition to this survey, the study coordinator or research assistant will periodically check in with the participant during the stimulation session to assess side effects.

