At the beginning of Sessions 2, 3 and 4, female participants will be asked if there is a possibility that they might be pregnant since Session 1. If the participants answer 'Yes' or 'Maybe', pregnancy test will be conducted. A pregnancy questionnaire will be used to document the answers.

Sayar, G. H., Ozten, E., Tufan, E., Cerit, C., Kaan, G., Dilbaz, N., & Tarhan, N. (2014). Transcranial magnetic stimulation during pregnancy. *Archives of women's mental health*, 17(4), 311-315.

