4 BASIC STUDY DESIGN

The design for this study is a pilot, randomized, double-blind, sham-controlled, crossover clinical trial which will be used to demonstrate feasibility and collect effectiveness data for further refinement of CF-tACS approach and for the subsequent design of a follow-up, multi-site, large scale study. We are seeking 24 healthy participants, both male and female, between the ages of 18-35. All women of child-bearing potential (defined as menstruating women of all ages) will be asked to take a pregnancy test during the initial session in order to determine eligibility for the study. We estimate 2 months to complete study enrollment.

The experimental design is a 3-treatment, 3-period, 3-sequence crossover with a 1 week washout interval between periods. N=24 participants will be enrolled and allocated by stratified randomization to six treatment sequences, S-At-Ad, S-Ad-At, At-S-Ad, At-Ad-S, Ad-S-At, Ad-At-S. S refers to Sham Regimen which is 40 minutes of sham CF-tACS, At refers to Active Theta-Gamma Frequency Regimen which is 40 minutes of verum CF-tACS, and Ad refers to Active Delta-Beta Frequency Regimen which is 40 minutes of verum CF-tACS.

Participants will be randomly assigned to one of 6 sequences on the first visit.

Sham treatment will include 10 seconds of ramp-in to 1 minute of CF-tACS with a ramp-out of 10 seconds for a total of 80 seconds of stimulation. The 80 seconds of stimulation serves to desensitize the scalp beyond which participants are generally not able to tell apart the presence or absence of stimulation. This strategy has been described in previous studies using tACS (Alekseichuk et al. 2017; Mellin et al. 2018). Verum CF-tACS will have a 10 second ramp-in and ramp-out with 5 minutes of stimulation, for 8 separate blocks with a minimum 3 minute break between each block, for a total of 2560 seconds of stimulation. Stimulation waveform is coupled frequency with a low frequency component and brief high frequency component on each cycle with maximum amplitude of 2 mA.

Eligible participants will have a total of 4 visits, each lasting approximately 3 hours and separated by at least 1 week. Total participation will include about 12 hours over the course of four weeks. All time estimates take into consideration breaks and time variance in administration.

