9.3 REFERRALS FOR MEDICAL FOLLOW-UP OR PSYCHOLOGICAL COUNSELING

There is a purely theoretical likelihood that stimulation of neuronal circuits can lead to epileptic discharge. To minimize this occurrence, we screen and exclude patients with personal and family history of neurological conditions from the study. If abnormalities or a seizure is witnessed during the course of the study, a referral will be made to the UNC Department of Neurology for follow-up. In the theoretical event that a seizure is witnessed that involves the loss of consciousness, the patient will be told not to operate a motor vehicle until cleared by the DMV.

To ensure participant comfort, a study coordinator or research assistant will periodically check in with the participant about any side-effects he/she may be experiencing during each stimulation session. Following the conclusion of the stimulation session, the participant will receive an Adverse Effects Questionnaire to report on any of the side-effects he/she may have experienced. This questionnaire reports side-effects on a likert scale (1=Absent, 2=Mild, 3=Moderate, 4=Severe). If the participant reports side-effects of Moderate to Severe intensity, a study coordinator or research assistant will discuss the side-effects experienced and note this response. If the participant has rated Severe discomfort, the participant will be withdrawn. The PI will be contacted based on the reported intensity on the Adverse Events Questionnaire and the participant's verbal confirmation of intensity.

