11.2 METHODS AND TIMING FOR ASSESSING, RECORDING, AND ANALYZING SAFETY PARAMETERS

11.2.1 ADVERSE EVENTS

All AEs, including local and systemic reactions not meeting the criteria for “serious adverse events”, will be captured on the appropriate CRF. In addition, the AE Report Form will be completed by the study coordinator (Appendix B). The AE Report Form includes the following:

- What is known about the therapy
- What is known about previous reported side effects
- If the AE occurred in temporal relation to the therapy
- Whether or not the AE improves or disappears when treatment is stopped
- Whether the AE is worsening of baseline symptoms
- Whether the AE is related to concurrent medical condition or medication use

Once complete, this form will be given to the PI and Co-I, who will review, comment, and sign this form. Completed forms will be placed in the participant’s folder.

In addition, the study coordinator will document any AE occurrence on the AE log (*Appendix D*), which includes information such as the date of the AE, severity, relationship to the treatment (assessed by the PI and Co-I*), actions taken, and outcome(s). The log will be reviewed and initialed by the PI 72 hours after being completed. All AEs occurring during the clinical trial will be documented appropriately regardless of relationship to CF-tACS. All AEs will be followed to adequate resolution and will be graded for severity and relationship to study treatment. Any medical condition noted at the initial session will be considered at baseline and not reported as an AE.

All AEs will be graded for severity using the following guidelines:

CONFIDENTIAL

- **ASYMPTOMATIC.** The participant is exhibiting no symptoms due to this event; no treatment needed.
- **MILD.** Event results in mild or transient discomfort, not requiring intervention or treatment; does not limit or interfere with daily activities (e.g., insomnia, mild headache)
- **MODERATE.** Event is sufficiently discomforting so as to limit or interfere with daily activities; may require interventional treatment (e.g., fever requiring antipyretic medication). In the case of a moderate AE, the medical advisor may recommend an over the counter medication.
- **SEVERE AND UNDESIRABLE.** Event results in significant symptoms that prevent normal daily activities; may require hospitalization or invasive intervention (e.g., anemia resulting in blood transfusion).

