11.4 TYPES AND DURATION OF FOLLOW-UP OF PARTICIPANTS AFTER ADVERSE EVENTS

The study coordinator will follow up within one week of an adverse event by a phone call.

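### Scheduled adverse-event collection covers only symptoms during the stimulation session, so events that start later are recorded only if the participant volunteers them

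*Combined protocol and SAP*

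**What the plan says.** Section 11.1 names the instrument and its timing: "A stimulation adverse effects questionnaire used in previous studies will be administered at the end of each stimulation session". It rates the "severity of symptoms experienced during the stimulation session". Section 9.3 gives the same timing: "Following the conclusion of the stimulation session, the participant will receive an Adverse Effects Questionnaire". The second scheduled check in 11.1 is that staff "will periodically check in with the participant during the stimulation session to assess side effects". Section 6.3 lists the questionnaire as the safety measure, and Appendix A marks it for Sessions 2, 3 and 4, with no column after them.

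Section 11.2.1 sets a wider scope: "All AEs occurring during the clinical trial will be documented appropriately regardless of relationship to CF-tACS". Its severity grades depend on how far the event disturbs daily activities, and insomnia is one of its examples of a mild event.

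Two other provisions reach beyond the session. Section 11.4 states: "The study coordinator will follow up within one week of an adverse event by a phone call". Section 3.2 states: "At the beginning of Sessions 2, 3 and 4, female participants will be asked if there is a possibility that they might be pregnant". The first depends on an AE that is already known. The second concerns pregnancy only, and only in women. The documents state no start or end for AE collection.

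**The concern.** A headache, a poor night, a skin reaction or a change of mood that starts after the participant goes home lies outside the questionnaire's recall period. No scheduled question asks about it at the next visit, and after Session 4 there is no next visit. Such events reach the AE log only by spontaneous report.

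Three things are at stake. First, the commitment in 11.2.1 has no procedure behind it for the time between sessions. Second, the 11.2.1 grades ask about daily life, which a form completed before leaving the laboratory can hardly show. Third, 10.4 lists a rise in event frequency among findings that might prompt a safety review, and a frequency built on volunteered reports is hard to interpret. Section 4 also intends the pilot to inform a larger multi-site study, whose planners would have systematic tolerability data for the sessions only.

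**Working it through.** The plan gives no figure on this point to reproduce. The check sets each source of AE information against the period it covers, then counts the periods left uncovered.

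**Coverage of each source**
- Questionnaire (6.3, 9.3, 11.1, Appendix A): the session just completed.
- Verbal check-ins (9.2, 9.3, 11.1): the session in progress.
- Question at the start of Sessions 2 to 4 (3.2): time since Session 1, pregnancy only, women only.
- Phone call (11.4): only after an AE is known.
- Reachability of staff by phone and email (3.3.2): any time, but the participant must take the initiative.

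Scheduled AE questions that cover onset after a session: 0.

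**Inputs for the count**
- Participants: 24 (Sections 3 and 4), all taken as completers.
- Visits: 4, at least one week apart (Section 4).
- Stimulation visits: 3, namely Sessions 2, 3 and 4 (6.2, Appendix A). Session 1 is taken as unstimulated, as 5.2 and Appendix A state.
- Sequences: the six listed in Section 4, "S-At-Ad, S-Ad-At, At-S-Ad, At-Ad-S, Ad-S-At, Ad-At-S".

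**Counts**
1. Scheduled questionnaires: 24 × 3 = 72, each limited to its own session.
2. Intervals after Sessions 2 and 3 with no general AE question: 24 × 2 = 48, each at least one week long.
3. Final sessions with no routine contact afterwards: 24 × 1 = 24.
4. Check: 48 + 24 = 72, so the gap follows every stimulation session.
5. Last regimen by sequence, in the order listed: Ad, At, Ad, S, At, S. Four of six are verum. With equal allocation (24 / 6 = 4 per sequence), 4 × 4 = 16 participants end on verum and 24 − 16 = 8 on sham.
6. Verum sessions: 24 × 2 = 48. Of these, 16 (16/48, one third) have no later scheduled contact. The other 48 − 16 = 32 are followed by a visit at which no AE question about the interval is scheduled.
7. The 48 intervals in step 2 therefore split into 32 after verum and 48 − 32 = 16 after sham.

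Equal allocation is an assumption, because Section 4 says only that randomization is stratified. In general, the number ending on verum is 24 minus the number assigned to At-Ad-S or Ad-At-S, which could lie anywhere from 0 to 24. The totals of 48 intervals and 24 final sessions do not depend on it.

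The interval from Session 1 to Session 2 (another 24 × 1 = 24) also has no AE question. It precedes any stimulation but lies within the trial, so 11.2.1 covers it.

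**The case against.** The strongest reply is that 11.2.1 is about recording. It says what is done with an AE once staff know of it, and it does not promise to seek AEs out. That is right. A reader might infer that 11.1 contradicts 11.2.1, but the two can both be followed. What remains is that nothing scheduled elicits the events that 11.2.1 would have recorded. Time after Session 4 may not even count as during the trial, since no AE window is defined. The gap is therefore firmest for the intervals after Sessions 2 and 3.

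A reader might also infer from 9.2 and 10.4 that the plan treats long-term harm to these participants as a concern that it then fails to follow up. The documents do not support this. Section 9.2 lists mild, transient effects and reports no serious ones. The phrase about short- or long-term effects in 10.4 concerns what studies might show about transcranial current stimulation, most naturally the wider literature.

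Nor does the crossover make attribution impossible. The AE log holds the date and the AE report form asks about temporal relation, so an event that is reported can be assigned to the right session. Volunteered events also enter the log whatever their cause, so the record is not strictly confined to in-session symptoms.

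Two points narrow the concern without removing it. Section 5.2 says that Sessions 2 to 4 repeat Session 1 apart from stimulation, and 6.1 describes the PANAS as covering affect in the past week, so mood might be captured between sessions. Appendix A, however, lists those scales for Session 1 only, and they are not AE instruments. Participants also receive a text the day before each session and can reach staff at any time, but neither is described as asking about AEs.

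Finally, no aim or outcome in 2.4 or Section 7 is a safety endpoint, and the device has a non-significant-risk designation (8.1). This limits the importance of the gap. The questionnaire form (Attachment 1) and the consent form are not available here and may carry reporting instructions. The recall period used above is the one that 11.1 describes.

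**Conclusion.** The point stands as a gap in ascertainment that is inexpensive to close. It is not a contradiction and not a threat to the pilot's stated aims. Scheduled AE collection covers the stimulation session and nothing after it: 48 intervals of at least one week after Sessions 2 and 3, plus 24 final sessions without routine follow-up, for 24 completers. The figure of 16 final verum sessions holds only under equal allocation.

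These are counts of uncovered periods, not of missed events. The documents give no rate of delayed events and no measure of how far volunteered reports fall short, so the loss cannot be quantified. The conclusion rests on the description of the questionnaire in 11.1 and on Appendix A being the complete schedule.

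**What to change.** In 11.1 and Appendix A:
- At the start of Sessions 2, 3 and 4, before stimulation, ask one open question about any health event since the last session. At Sessions 3 and 4, add the existing symptom list, applied to that interval.
- For each event, record the onset date and the code of the preceding session. Using the code and not the condition keeps staff blinded.
- State the AE collection window as running from consent at Session 1 to the last scheduled contact. A window that began at first stimulation would leave out the week or more between Sessions 1 and 2 and so narrow 11.2.1.
- Optionally, make one short call to every participant about a week after Session 4. This would be a new routine contact, because the 11.4 call is tied to a known AE. A week matches the minimum spacing between visits.

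The cost is a few minutes at each of three existing visits, new entries in Appendix A and, if the option is taken, up to 24 short calls by existing staff. The downside is that some unrelated events will be recorded and will need an AE form.

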11.2 METHODS AND TIMING FOR ASSESSING, RECORDING, AND ANALYZING SAFETY PARAMETERS

11.2.1 ADVERSE EVENTS

All AEs, including local and systemic reactions not meeting the criteria for “serious adverse events”, will be captured on the appropriate CRF. In addition, the AE Report Form will be completed by the study coordinator (Appendix B). The AE Report Form includes the following:

- What is known about the therapy
- What is known about previous reported side effects
- If the AE occurred in temporal relation to the therapy
- Whether or not the AE improves or disappears when treatment is stopped
- Whether the AE is worsening of baseline symptoms
- Whether the AE is related to concurrent medical condition or medication use

Once complete, this form will be given to the PI and Co-I, who will review, comment, and sign this form. Completed forms will be placed in the participant’s folder.

In addition, the study coordinator will document any AE occurrence on the AE log (*Appendix D*), which includes information such as the date of the AE, severity, relationship to the treatment (assessed by the PI and Co-I*), actions taken, and outcome(s). The log will be reviewed and initialed by the PI 72 hours after being completed. All AEs occurring during the clinical trial will be documented appropriately regardless of relationship to CF-tACS. All AEs will be followed to adequate resolution and will be graded for severity and relationship to study treatment. Any medical condition noted at the initial session will be considered at baseline and not reported as an AE.

All AEs will be graded for severity using the following guidelines:

CONFIDENTIAL

- **ASYMPTOMATIC.** The participant is exhibiting no symptoms due to this event; no treatment needed.
- **MILD.** Event results in mild or transient discomfort, not requiring intervention or treatment; does not limit or interfere with daily activities (e.g., insomnia, mild headache)
- **MODERATE.** Event is sufficiently discomforting so as to limit or interfere with daily activities; may require interventional treatment (e.g., fever requiring antipyretic medication). In the case of a moderate AE, the medical advisor may recommend an over the counter medication.
- **SEVERE AND UNDESIRABLE.** Event results in significant symptoms that prevent normal daily activities; may require hospitalization or invasive intervention (e.g., anemia resulting in blood transfusion).

Changes in the severity of an AE will be documented with the Note to File document (Appendix E) and will be filed in the participant's folder.

***Relationship to Study Products:** The PI will determine whether an AE is associated with the study treatment. The event will be labeled associated if the event is temporally related to the administration of a therapy and no other factors can explain the event. The event will be labeled as not associated if the event is temporally independent of the study treatment and can be explained by external factors, such as major life events.

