11.2.3 UNANTICIPATED PROBLEMS

Unexpected Events (UE) will be recorded on the UE/SAE log (Appendix D) and will include information such as the date of the event, when the study team was informed of this event, details of the event, when the IRB was notified, and whether the SAE form was completed. The IRB will be notified of each UE that may occur during the study.

The Office for Human Research Protections (OHRP) considers unanticipated problems involving risks to subjects or others to include, in general, any incident, experience, or outcome that meets all of the following criteria:

- unexpected (in terms of nature, severity, or frequency) given (a) the research procedures that are described in the protocol-related documents, such as the IRB-approved research protocol and informed consent document; and (b) the characteristics of the subject population being studied;
- related or possibly related to participation in the research (in the guidance document, possibly related means there is a reasonable possibility that the incident, experience, or outcome may have been caused by the procedures involved in the research); and
- suggests that the research places subjects or others at a greater risk of harm (including physical, psychological, economic, or social harm) than was previously known or recognized.

If an UE occurs the IRB will be notified and the study will be adjusted as needed to protect the health and safety of the participants. Depending on the nature of the UE, the research protocol, inclusion/exclusion criteria, and informed consent will be changed to reflect the possibility of this event reoccurring. During this time, no new participants will be recruited and the research procedures for currently enrolled participants will be stopped. Each UE will be recorded and reported throughout the study.

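### The adverse-event causality rule gives no label in two of four cases, and its only positive label is stricter than the protocol's own possibly-related and suspected thresholds

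*Combined protocol and SAP*

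**What the plan says.** Section 11.2.1 (Adverse Events) asks for each adverse event to receive a severity grade and a grade for its relationship to treatment. The paragraph on relationship to study products, at the end of that section, gives the rule. An event is labelled associated if it is "temporally related to the administration of a therapy and no other factors can explain the event". It is "labeled as not associated if the event is temporally independent of the study treatment and can be explained by external factors". No third category and no default is given.

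Three other places bear on this:

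- Section 11.2.3 (Unanticipated Problems) sets its causality test at "related or possibly related to participation in the research", and explains that possibly related requires only a reasonable possibility of causation.
- Section 11.3 (Reporting Procedures) attaches a 7-day limit to serious adverse reactions that are unexpected and suspected.
- Section 11.1 (Safety Parameters) has participants rate how far they believe their side effects relate to stimulation, on a five-point scale: "1 = no relation, 2 = remote, 3 = possible, 4 = probable, 5 = definite".

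The assessor is described in two ways within 11.2.1. The log entry covers "relationship to the treatment (assessed by the PI and Co-I"; the rule itself says "The PI will determine whether an AE is associated with the study treatment".

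**The concern.** Each label needs two conditions at once, and the two labels are not complements of each other. Many events will meet one condition of each and so fall between them. The events most exposed to this are foreseeable here. The side-effect list in 11.1 includes headache, sleepiness and difficulty concentrating, and visits last about three hours (Section 4) with eight task blocks. For such an event during a session, an investigator could often point to another possible cause without being able to call the event independent of stimulation in time.

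What is at stake is whether the relationship entry in the adverse-event log can be used. The trial is meant to inform a larger multi-site study (Section 4). If the entry is left blank, or filled by each assessor's own convention, later readers cannot tell which events were possibly related. The label would also not tell the investigator whether an event meets the thresholds in 11.2.3 and 11.3, where the category reached affects how soon the IRB is told.

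**Working it through.** No sample size, power or event figure enters, so the check is an enumeration followed by a comparison of thresholds.

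Inputs, both from the relationship paragraph of 11.2.1: let T mean that the event is related in time to stimulation, and E that another factor can explain it.

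- *Associated* = T and not-E.
- *Not associated* = not-T and E.

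Two yes/no criteria give 2 × 2 = 4 combinations:

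| Related in time (T) | Other explanation (E) | Label under 11.2.1 |
|---|---|---|
| Yes | No | Associated |
| No | Yes | Not associated |
| Yes | Yes | None |
| No | No | None |

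Labelled: 2 of 4. Unlabelled: 4 − 2 = 2 of 4. The requirement to grade every event for relationship therefore cannot be met from the rule in half of the combinations. This is a share of combinations, not of events; the documents give no rate from which a share of events could be worked out.

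Comparison of thresholds:

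- 11.2.1, *associated*: every other explanation must be ruled out.
- 11.2.3, *possibly related*: a reasonable possibility of causation is enough; other causes need not be excluded.
- 11.3, *suspected*: not defined in the section, but on its ordinary meaning it does not require other causes to be excluded.

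An event with T = yes and E = yes is the usual candidate for *possibly related*. It fails *associated* because E is yes, and fails *not associated* because T is yes. So the row where 11.2.3 would most often apply is one of the two rows where 11.2.1 is silent.

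Direction of any error: if unlabelled events are treated as not associated, or if the *associated* entries are read as the full set of possibly related events, the log under-counts. If the assessor resolves unlabelled events towards associated, it does not. The text does not say which will happen.

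**The case against.** A reader might infer that the rule systematically attributes too few events to stimulation, that expected effects could never be counted as associated, or that possibly related events have no way into the unanticipated-problem test. The documents do not support any of these.

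- The rule leaves an event with both features unlabelled; it does not call it not associated. The text also says when the label applies, without saying that it applies only then. Under-attribution needs a default that is nowhere stated.
- Skin sensations or redness at the electrode site can be related in time with no other explanation, and would then be labelled associated.
- 11.2.3 carries its own definition and does not take the 11.2.1 label as an input. The adverse-event report form (Appendix B) collects relevant facts: timing, improvement on stopping, worsening of baseline symptoms and concurrent causes.
- Adverse events are documented whatever their relationship to stimulation (11.2.1), all serious events go to the IRB (11.2.2), and so does each unexpected event (11.2.3). None of this turns on the label.
- Neither the outcomes in Section 7 nor the analysis plan in 12.2 tabulates the label, so there is no planned tolerability summary for it to bias. The questionnaire given after each stimulation session yields severity and relatedness ratings that do not pass through it.

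All of this stands, and it limits the consequence. It does not fill the two empty rows. The recording and notification rules do not produce a causality grade. The five-point rating is the participant's belief, and nothing links it to the relationship entry in the log. The log form itself was not in the copy read for this review, so whether it offers further categories could not be checked; if it does, the text of 11.2.1 should say so.

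**Conclusion.** The point holds as a gap in classification. The rule in 11.2.1 labels two of four combinations, cannot deliver the relationship grade that the same section requires, and has a single positive label stricter than, and not mapped to, the thresholds in 11.2.3 and 11.3. The section also names the assessor inconsistently.

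Possibly related events may be under-counted in the log under either of the two readings described above. That is a risk, and its size cannot be given. The conclusion assumes that the two definitions are meant to be applied as written and that the log has no further categories. It is a minor safety-classification correction and does not touch the planned efficacy analysis.

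**What to change.** Replace the two labels in 11.2.1 with an exhaustive graded scale. The five levels already in 11.1, from no relation to definite, would serve, assigned by the investigator blind to stimulation condition. A stated default or a single added middle label would also close the gap; the five-level scale has the advantage of already being in the protocol.

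State that a rating of *possible* or higher meets the possibly-related criterion in 11.2.3 and the suspected criterion in 11.3. Make this one-way: 11.2.3 covers participation in the research as a whole, so an event rated below *possible* for stimulation may still qualify through another study procedure.

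Reconcile who assigns the grade, since 11.2.1 names the PI and Co-I in one place and the PI in another, and align the relationship field of the adverse-event log.

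The cost is protocol and log wording, with no added staff or procedures. The small downside is that more events will be listed as possibly related.
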